3.7 Exploratory Endpoints

- 1. Disability improvement response rate on the T25FW, 9HPT, either hand, and EDSS at Weeks 12, 24, 36, and 52, and the EDSS + at Weeks 12, 24, and 36.
- 2. Change from Baseline on the T25FW and 9HPT, either hand, at Weeks 12, 24, 36, and 52
- 3. Disability progression response rate on the EDSS+ (T25FW, 9HPT, either hand, EDSS) and for each EDSS + component
- 4. 12- and 24-week confirmed disability improvement response rate on the EDSS + (T25FW, 9HPT, either hand, EDSS) and for each EDSS + component
- 5. Change from Baseline on the MS Impact Scale (MSIS-29) version 2 at Weeks 12, 24, 36, and 52
- 6. Change from Baseline on the Modified Fatigue Impact Scale (MFIS) at Weeks 12, 24, 36, and 52
- 7. Change from Baseline on cognition battery at Weeks 12, 24, 36, and 52:
 - Symbol Digit Modalities Test (SDMT) Oral Version
 - Brief Assessment of Cognition Verbal Memory Immediate Recall BAC App Version

- Brief Assessment of Cognition Tower of London BAC App Version
- Change from Baseline on the Low Contrast Visual Acuity (LCVA) assessments at Weeks 12, 24, 36, and 52
- 9. Change from Baseline in plasma biomarkers at Weeks 12, 24, 36, and 52
- 10. Change from Baseline on the MS Individualized Outcome Assessment (Multiple Sclerosis Individualized Outcome Assessment [MSIOA]) scale at Weeks 24 and 52
- 11. Change from Baseline in one week average daily step count and other activity measures (via home actigraphy with wearable biosensor) initiated at Weeks 24, 36, and 52

MRI Endpoints

The following imaging tests will be conducted. Details will be provided in the Statistical Analysis Plan (SAP).

- Lesion counts and volumes
- Brain and spinal cord atrophy measures
- Magnetization transfer ratio (MTR)
- Diffusion tensor imaging (DTI)

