7.3 Statistical Analyses for Efficacy

The ORS scores will be summarized descriptively (including n, mean, standard deviation, minimum, median, and maximum) along with the 95% confidence interval at each visit. The frequency and percentage of ORS for –4 to +4 will also be provided by treatment group at each visit. The ORS for each treatment group at scheduled visits and overall will also be estimated using a mixed-effect model for repeated measures (MMRM) including treatment group, visit, treatment-by-visit interaction, and stratification factors as fixed effects, with the baseline values for the ORS components as covariates.

For other continuous efficacy endpoints, the mean, standard deviation, median, minimum and maximum will be reported for each treatment group. The treatment comparison will be conducted using MMRM model including treatment group, visit, treatment-by-visit interaction, and stratification factors as fixed effects and the baseline value associated with the endpoint as a covariate.

For binary efficacy endpoints, the frequency and percentage will be provided by treatment group. The treatment comparison will be conducted using a logistic regression model adjusted for the stratification factors and baseline score associated with the endpoint.

All efficacy endpoints will be analyzed on mITT population. The RF and MMIA Sets will be used for the primary and other efficacy analyses as specified in the SAP.

Sample Size Estimation

Approximately 165 subjects will be equally randomized 1:1:1 (55 subjects in each treatment group, with a target of 20 SPMS subjects and approximately 35 RRMS subjects per treatment group). There are limited prior data to estimate the magnitude of effect and variance for a neurorestorative therapy. The sample size was therefore selected based on operational feasibility, variance seen in prior MS trials, and the likelihood of predicting success in subsequent phases of development.

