2.1 Individual Treatment Period Visit Activities

This section presents a list of activities performed during each visit, organized by visit.

Study procedures may be split over 2 consecutive days, with the study drug administration to occur on the second day. At the Week 0 Baseline Visit, the site will conduct actigraphy training with the subject, and application of sensors should be done on the same day as the timed 25-foot walk. These activities (along with all the pre-dose activities) should occur before dosing.

Activities are grouped by category (Interview, Exam, etc.). Further information about each activity is provided in Section 3.

COVID-19 Pandemic-Related Acceptable Protocol Modifications

During the COVID-19 pandemic, if it is not possible for all study procedures to be performed as specified due to travel restrictions or other reasons, the following modifications are allowed:

- Some study visits and/or activities may be performed by phone/virtually. These are indicated by a hashtag (#) in the appropriate visit table(s) below.
 - During a virtual visit, activities that do not need to be performed are indicated by a minus sign (-).
- Some study visits and/or activities may be performed by a local laboratory. These are indicated by a plus sign (+) in the appropriate visit table(s) below. All procedures performed at local facilities must be performed by appropriately qualified personnel.
- Study Visits and/or activities should be performed as scheduled whenever possible. If it is not possible to do so due to the pandemic, the following modifications are allowed:
 - Study procedures may be split over 7 consecutive days. The Expanded Disability Status Scale (EDSS), 9-Hole Peg Test (9HPT), or Timed 25 Foot Walk (T25FW) should all occur on the same visit day.
 - MRI assessments may be collected up to 12 weeks after the projected visit for the missed timepoints at Week 24 and 52 with the sponsor's consent due to reasons related to the COVID-19 pandemic. However, all MRI assessments projected to be obtained on or before mid-November 2020 must be completed by the end of November 2020. To accommodate scheduling of the vast volume of projected Week 52 MRIs in December 2020, at the discretion of the sponsor, sites may schedule Week 52 MRIs up to -28 days of their projected Week 52 visit.

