4.7 Missing Data Imputation

For continuous efficacy variables, data will be summarized using a mixed-effect model for repeated measures (MMRM) model unless otherwise specified. Missing data will not be imputed before applying an MMRM model. The MMRM model relies on a missing at random (MAR) assumption.

For sensitivity analyses of the primary and secondary efficacy variables, missing values will be imputed using multiple imputation (MI) and categorized as responder/non-responder after imputation. The MI model also relies on a MAR assumption.

Justification for the MAR Assumption:

The COVID-19 pandemic is interfering with the conduct of many ongoing trials, with potential impact on treatment duration and the collection, analysis and the interpretation of clinical trial data. Some protocol-specified visits in this clinical trial may be impacted due to COVID-19 infection or logistical restrictions during the pandemic. For example, some scheduled visits may be missed due to self-quarantine or local government restrictions on travel; some visits may also be delayed or canceled due to healthcare resource constraints during the pandemic. These missed visits will be recorded in the

database. The probability of having missed visits and missing data due to COVID-19 infection or logistical restrictions related to the COVID-19 pandemic can be reasonably assumed to be unrelated to the unobserved values conditional on the observed data.

Therefore, for the purpose of statistical analysis, it is reasonable to assume that these missing data are missing at random (MAR) and the statistical models that require MAR assumption are appropriate. In some cases, sensitivity analyses may be performed to assess the impact of missing data and the robustness of the conclusion.

Where noted, summaries as observed will not impute values for missing evaluations, and thus a subject who does not have an evaluation on a scheduled visit will be excluded from the as observed for that visit.

Safety variables will be summarized as observed.

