9.4 Other Efficacy Analyses

Change from baseline treatment comparison at each visit will be conducted using an MMRM model including treatment group, visit, treatment-by-visit interaction, and stratification factors as fixed effects, the baseline values associated with the endpoint as covariates. The REPEATED statement will be used for visit with blocks in the covariance matrix identified by subject nested within treatment group. The unstructured covariance structure will be used to estimate the within subject variance-covariance. If the model fails to converge, the first order autoregressive (AR[1]) covariance structure will be substituted. If the model still fails to converge, the compound symmetry (CS) covariance structure will be substituted. Denominator degrees of freedom will be computed using the Kenward-Roger method.

For binary efficacy endpoints, the frequency and percentage will be provided by treatment group unless otherwise noted.

9.4.1**Confirmed Improvement on the EDSS + and its components**

Confirmed 12-week disability improvement on the EDSS + or components of the EDSS + indicates a subject has clinically significant improvement at a visit as well as the next visit for one or more EDSS+ components, or if the next visit is missing, the subsequent visit. Confirmation may include assessments collected in the post-treatment follow-up period. The improvement confirmation must be in the same component of the EDSS +. If a subject has improvement in more than one component of the EDSS +, the subject must have confirmation in at least one of the same components to be considered as having confirmed disability improvement. For example, if a subject has clinically significant improvement in the T25FW at Week 12, the subject must have clinically significant improvement in the same component of the EDSS + at Week 24 (or if Week 24 is missing, Week 36) to be considered to have confirmed improvement.

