9.4.11 MRI Parameters

The MRI parameters of interest and analyses are listed in Section [4.3.3](#).

The number and percentage of subjects with active lesions will be summarized for T1 GAD-enhancing lesions and T2 hyperintense lesions (separately). The difference in the proportion between elezanumab and placebo groups with the 95% confidence interval for the difference based on Wald confidence limits will be presented.

The cumulative number of total T1 GAD-enhancing lesions, cumulative number of total T2 hyperintense lesions, cumulative number of post-baseline T1 GAD-enhancing lesions, cumulative number of post-baseline new and enlarging T2-lesions, will be summarized with continuously and analyzed using an analysis of covariance (ANCOVA). The model for the analysis of the cumulative number of total lesions will include treatment, the stratification factors of diagnosis of MS (RRMS or rSPMS) and background MS immunotherapy (Yes or No). For the cumulative number of lesions during the treatment period, only subjects with Baseline, Week 24, and Week 52 MRIs will be included. For the cumulative number of lesions post-baseline, only subjects with Week 24 and Week 52 will be included.

The number of T1 GAD-enhancing lesions at each visit (Baseline, Week 24, Week 52) will be summarized categorically with the number and percent of subjects for the following categories: 0, 1, 2, 3, 4, 5, > 5.

The following endpoints will be analyzed using change or percent change from baseline using an ANCOVA model.

- Change from Baseline in total volumes of T1 GAD-enhancing lesions
- Change from Baseline in total volume of T2 hyperintense lesions
- Percent change from Baseline in whole brain, gray matter (GM), thalamus, white matter (WM) and normal appearing white matter (NAWM) volumes
- Change from Baseline in regional magnetization transfer ratio (MTR) parameters for whole brain, and NAWM, and MTR for T2 lesions

- Change from Baseline in diffusion tensor imaging (DTI) parameters (fractional anisotropy and Apparent Diffusion Coefficient (ADC)) for whole brain, NAWM and T2 hyperintense lesions
- Change from Baseline in cervical spinal cord area, volume and number of lesions
- Change from Baseline in regional MTR for cervical spinal cord lesions
- Change from baseline in DTI parameters (fractional anisotropy and ADC) for cervical spinal cord

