The model for the change from baseline analysis will include treatment, the stratification factors of diagnosis of MS (RRMS or rSPMS) and background MS immunotherapy (Yes or No), and the baseline value. For each treatment group, the number of subjects, mean, standard deviation, minimum, and maximum, will be presented, as well as the LS means and standard error, and the between group difference, standard error, and 95% confidence interval.

The change from baseline in lesion MTR for T1 GAD-enhancing lesions and delta MTR will be analyzed using an MMRM. The change from baseline will be calculated for each unique lesion within a treatment group. A dummy code will be created based on each subject-lesion to describe each unique lesion. The model will include the fixed effects of treatment, visit, the stratification factors of diagnosis of MS (RRMS or rSPMS) and background MS immunotherapy (Yes or No), and the treatment-by-visit interaction, with baseline MTR value as a covariate. The RANDOM statement will be used for each subject. The REPEATED statement will be used for visit with blocks in the covariance matrix identified by unique lesion nested within subject nested within treatment group. The unstructured covariance structure will be used to estimate the within subject variance-covariance. If the model fails to converge, the first order autoregressive (AR[1]) covariance structure will be substituted. If the model still fails to converge, the compound symmetry (CS) covariance structure will be substituted. Denominator degrees of freedom will be computed using the Kenward-Roger method.

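### SAP 9.4.11 analyses the subject-level MRI change endpoints by an ANCOVA with no visit term, so a Week 52 comparison ignores the Week 24 scan of anyone without a Week 52 value; an MMRM would recover a modest amount of information at almost no cost

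*SAP*

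**What the plan says.** SAP 9.4.11 introduces its list of subject-level imaging endpoints with: "The following endpoints will be analyzed using change or percent change from baseline using an ANCOVA model". The terms follow: "The model for the change from baseline analysis will include treatment, the stratification factors of diagnosis of MS (RRMS or rSPMS"), then background immunotherapy and the baseline value. No visit effect, treatment-by-visit interaction or within-subject covariance is named. Operations Manual 3.17 schedules scans at Screening (serving as baseline), Week 24, and Week 52 or Early Discontinuation.

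Elsewhere the default is a repeated-measures model:

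- SAP 4.7: "For continuous efficacy variables, data will be summarized using a mixed-effect model for repeated measures (MMRM) model unless otherwise specified".
- SAP 9.4: "Change from baseline treatment comparison at each visit will be conducted using an MMRM model including treatment group, visit, treatment-by-visit interaction".
- Protocol 7.3, for continuous efficacy endpoints other than ORS: "The treatment comparison will be conducted using MMRM model including treatment group, visit, treatment-by-visit interaction, and stratification factors".

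Protocol 3.7 leaves the imaging detail to the SAP. In SAP 9.4.11 itself, MTR of T1 gadolinium-enhancing lesions and delta MTR are analysed by MMRM. MSIOA, whose only post-baseline time points are also Weeks 24 and 52, is analysed by MMRM under SAP 9.4.5.

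Multiple imputation (SAP 4.7, 9.3.1 and 9.4.2) covers the primary and secondary variables, confirmed EDSS+ improvement and EDSS+ progression. No missing-data method is stated for MRI.

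**The concern.** With two post-baseline scans and no visit term, the natural reading is one ANCOVA per visit. The Week 52 comparison then uses only subjects with a Week 52 value. A Week 24 scan from a subject who lacks the later one is collected but not used.

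There are two consequences. The first is lost precision. The second is a mismatch with SAP 4.7, which argues that pandemic-related missingness is unrelated to unobserved values once the observed data are taken into account. For imaging, the observed data include the Week 24 scan. An MMRM conditions on it; this ANCOVA conditions only on baseline and strata.

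Missing scans are a realistic prospect. The Operations Manual visit tables drop the MRI when the Week 24 or Week 52 visit is held virtually, and SAP 11.1 refers to increased missing data. The SAP gives no reason for choosing ANCOVA here. Having only two post-baseline visits cannot be the reason, since MSIOA has the same two and gets an MMRM.

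At stake is the precision, and to a lesser degree the robustness, of the imaging evidence in a study with about 55 subjects per arm.

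**Working it through.** **Inputs from the documents.** 55 per arm, effect size 0.43, one-sided significance level 0.1 and about 10% overall dropout (all SAP 4.4); post-baseline scans at Weeks 24 and 52 (Operations Manual 3.17).

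**Assumptions.** The share m without a Week 52 scan, taken as 10% (the SAP's dropout figure), 20% and 30%; the Week 24 to Week 52 residual correlation ρ, taken as 0.3 to 0.9; everyone has a Week 24 scan, which is the case most favourable to MMRM. The documents give neither ρ nor a missing-scan rate for MRI.

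**Step 1: the plan's own figure.** 55 × 0.9 = 49.5 per arm. Power = Φ(0.43 × √(49.5/2) − 1.282) = Φ(0.858) = 0.804; the noncentral t gives 0.802. The stated 80% is reproduced. It concerns ORS and is used here only as the source of the 10%.

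**Step 2: variance at Week 52.** With residual variance σ² and n subjects per arm:

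- Week 52-only ANCOVA: σ² / [n(1 − m)]
- Likelihood model using Week 24: (σ²/n) × [ρ² + (1 − ρ²)/(1 − m)]
- Ratio, second to first: (1 − ρ²) + ρ²(1 − m) = 1 − mρ²

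The gain in effective sample size is 1/(1 − mρ²) − 1:

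| m | ρ = 0.3 | ρ = 0.5 | ρ = 0.7 | ρ = 0.9 |
|---|---|---|---|---|
| 10% | 0.9% | 2.6% | 5.2% | 8.8% |
| 20% | 1.8% | 5.3% | 10.9% | 19.3% |
| 30% | 2.8% | 8.1% | 17.2% | 32.1% |

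Example: m = 0.2, ρ = 0.7 gives 1 − 0.2 × 0.49 = 0.902, and 1/0.902 = 1.109. Per arm at 10% missing, the 49.5 subjects in the ANCOVA become worth 50.8, 52.1 or 53.9 for ρ = 0.5, 0.7 or 0.9. At 20% missing, 44.0 become 46.3, 48.8 or 52.5.

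A simulation (4,000 trials, 55 per arm, missingness unrelated to outcome) gave variance ratios, ANCOVA to likelihood model, of 1.056 (m = 10%, ρ = 0.7), 1.136 (20%, 0.7) and 1.167 (20%, 0.9). The formula gives 1.052, 1.109 and 1.193, so they agree to within 3%.

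**Step 3: bias in the treatment difference.** True Week 52 difference 0.43, ρ = 0.7:

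| Missingness at Week 52 | ANCOVA | Likelihood model |
|---|---|---|
| Unrelated to Week 24 | 0.43 | 0.43 |
| Depends on Week 24 deviation from expected value, same in both arms | 0.43 | 0.43 |
| Depends on the Week 24 result, same in both arms, Week 24 effect 0.2 SD, about 10% missing | 0.42 | 0.43 |
| Only the active arm loses poor Week 24 results, about 12% missing overall | 0.52 | 0.43 |
| As above, about 22% missing overall | 0.57 | 0.42 |

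ANCOVA goes materially wrong when the dependence differs by arm. It drifts slightly when the dependence is common to both arms but a treatment effect is already present at Week 24.

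**The case against.** **ANCOVA is permitted.** SAP 4.7 allows exceptions to its MMRM default, SAP 9.4.11 makes one, and Protocol 3.7 defers imaging detail to the SAP. A reader might infer a contradiction between protocol and SAP; there is none. Nor is MMRM universal elsewhere: cumulative lesion counts and the multiple-imputation analysis of ORS use ANCOVA, and most LCVA measures are descriptive. This stands.

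**Visit-by-visit fitting is an inference.** It follows from the absent visit term and is not written. This stands, and is a reason for the SAP to say so.

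**Exclusion of those who stop early is not established.** A reader might infer that subjects who leave after Week 24 with worsening scans are lost. But a scan is scheduled at Early Discontinuation, with the visit-table notes referring to more than 4 weeks since the last MRI. The pandemic rule is also a recovery provision: "MRI assessments may be collected up to 12 weeks after the projected visit for the missed timepoints at Week 24 and 52", and Week 52 scans may be up to 28 days early. Such scans may supply some final values. The SAP gives no mapping to Week 52, so neither inclusion nor exclusion can be assumed.

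**Validity does not require missingness to be independent of the Week 24 result.** Step 3 shows little or no bias in the treatment difference when the dependence is the same in both arms. The documents give no sign of differential dropout, and SAP 4.7 attributes the missingness to pandemic logistics. This stands as a limit on the bias argument; the efficiency argument is unaffected.

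**The gain is small and the endpoints are exploratory.** True at 10% missing. Subjects with neither scan help neither model.

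**Conclusion.** The point holds as a low-severity improvement. The listed ANCOVA, read visit by visit, leaves Week 24 scans unused at Week 52 and conditions on less than the SAP's own missing-at-random argument presupposes. At about 10% missing, the gain from an MMRM is roughly 3% to 9% in effective subjects for correlations of 0.5 to 0.9; at an assumed 20% it is roughly 5% to 19%. These figures assume complete Week 24 scans and no Week 52 value from an Early Discontinuation or late scan, so they are upper values for a given m and ρ.

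Material bias requires missingness that depends on Week 24 results differently by arm, or a Week 24 treatment effect combined with steep dependence. The documents suggest neither.

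It would be tempting to call the imaging analysis invalid or a departure from the protocol. The documents do not support that: the choice is prespecified and allowed, and no primary or secondary result depends on it.

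**What to change.** In SAP 9.4.11, analyse the listed change and percent-change endpoints with one MMRM over Weeks 24 and 52: treatment, visit, treatment-by-visit, both stratification factors, baseline and baseline-by-visit, with unstructured covariance and Kenward-Roger degrees of freedom. The baseline-by-visit term is not in the SAP 9.4 model. It is added so that each visit keeps its own baseline slope, as separate ANCOVAs would allow; with complete data the Week 52 estimates should then be essentially those of the ANCOVA.

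State in the same section how Early Discontinuation scans, scans up to 12 weeks late and scans up to 28 days early are assigned to Week 24 or Week 52. If ANCOVA is kept, state that it is fitted at each visit, give the reason, and add a rule for missing scans.

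The cost is a few lines of SAP text and a small change to existing code. Protocol Appendix E reports that a planned efficacy analysis has already taken place. If the imaging ANCOVA has been run, keep it as prespecified and report the MMRM as a labelled supplementary analysis.

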9.5 Efficacy Subgroup Analyses

Subgroup analysis for the primary endpoint (ORS) based on the mITT analysis set will be conducted by the subgroups specified in Section 5.2. This will be based on the MMRM analysis and the analysis will be presented for Week 12, 24, 36, and 52. The model will include the fixed effects of treatment, visit, the stratification factors of diagnosis of MS (RRMS or rSPMS) and background MS immunotherapy (Yes or No), subgroup, treatment-by-visit interaction, treatment by subgroup interaction, and treatment by subgroup by visit interaction with baseline EDSS, T25FW, 9HPT-D and 9HPT-ND values as covariates. The REPEATED statement will be used for visit with blocks in the covariance matrix identified by subject nested within treatment group. The unstructured covariance structure will be used to estimate the within subject variance-covariance. If the model fails to converge, the first order autoregressive (AR[1]) covariance structure will be substituted. If the model still fails to converge, the compound symmetry (CS) covariance structure will be substituted. Denominator degrees of freedom will be computed using the Kenward-Roger method.

